7. STUDY PROCEDURES

All non-investigational procedures will be according to the common practice at each site and determined by the treating physician. Procedures such as routine hospital examinations, brain CT scan or MRI will be performed according to each site's standard management protocol and will be properly documented in the patient's medical records.

7.1 Study

Study flow of Subjects through the TIGER Study is illustrated in Figure 2.

[figure not shown]

Figure 2. Study Flow

7.2 Screening and Baseline Visit

Screening against study inclusion/exclusion criteria will be completed to determine potential eligibility. Subject screening will be documented on the site specific Screening & Enrolment Log. For patients/LARs who choose not to participate, the reason for non-participation will also be documented.

7.2.1 General Medical Evaluation

- Physical examination and medical history (including time last known well and time symptoms first observed)
- Prior/Concomitant Medications
- Vital signs (Blood pressure and pulse)

7.2.2 Laboratory Evaluation

Blood and/or urine specimens for the following Clinical Laboratory tests:

- Pregnancy (females of childbearing age)
- Hemoglobin, platelet count per site standard of care (SOC)
- Prothrombin time (PT)/International normalized ratio (INR) and partial thromboplastin time (PTT) per site SOC.
- Creatinine or Glomerular Filtration Rate per site SOC
- Serum glucose

Note: Study informed consent not required for lab tests required as per the SOC in assessing acute ischemic stroke treatment.

7.2.3 Neurologic Evaluation

National Institutes of Health Stroke Scale (NIHSS) recorded at screening along with pre-stroke mRS obtained from the Subject or their caretaker. NIHSS and mRS will be performed by certified Study personnel.

7.2.4 Imaging (Brain CT or MRI)

CT or MRI will be used to confirm eligibility. Patients with metal implants or other contraindications to MR will utilize CT exclusively. Baseline imaging will be used to confirm:

1. For anterior circulation strokes, baseline Alberta Stroke Program Early Computed Tomography Score (ASPECTS) of 6-10 on NCCT or CTA-source images, or DWI MR lesion volume ≤ 50 ml.
2. For posterior circulation strokes, pcASPECTS 8-10, on CTA-source images or diffusion MRI
3. No evidence of acute intracranial hemorrhage on presentation
4. No evidence of significant mass effect with midline shift
5. No evidence of intracranial tumor (apart from small meningioma, ≤ 2 cm in diameter)

6. No evidence of cerebral vasculitis
7. No evidence of bilateral stroke or stroke in multiple territories (e.g. Bilateral anterior circulation, anterior/posterior circulation)
8. No evidence of target vessel aneurysm

Subjects who underwent a CT or MRI at a referring hospital and then were transferred to the study hospital for further treatment will need to undergo another CT or MRI at the study hospital to ensure continued absence of extended infarct or acute hemorrhage.

7.2.5 Screen Failures

Subjects who do not satisfy all the inclusion/exclusion criteria prior to signing the ICF will be considered pre-screen failures. If a Subject satisfies initial inclusion/exclusion criteria and has been consented but does not satisfy additional study inclusion/exclusion criteria at time of diagnostic angiography (such as excessive vessel tortuosity evident by angiography), the Subject will be considered a screen failure. Screen fails will receive medical treatment per standard of care and will not enter into the trial population.

7.3 Procedure

7.3.1 Angiography

Diagnostic catheter angiography will be conducted prior to device deployment to confirm inclusion/exclusion criteria and to determine location of occlusion. Diagnostic angiograms will also be obtained after each Tigertriever device pass (maximum of 3) and each pass of rescue therapy. An angiogram will be considered for primary endpoint assessment where a rating of mTICI 2b or greater reperfusion is achieved (for 3 or less passes of the Tigertriever device) or after the third pass of the Tigertriever device. A final post-procedure angiogram (full A-P lateral image) will be obtained once all treatments have concluded, including rescue therapy, if necessary. All images are to be de-identified and submitted to the core lab for review:

The University of California at Los Angeles with the following address:

Angiography and Noninvasive Imaging Core Lab
[name], FAAN, FAHA, FANA
UCLA Department of Neurology
Neuroscience Research Building
[name]
[name]

7.3.2 Device Preparation, Delivery, & Positioning

1. Administer anti-coagulation and anti-platelet medications per SOC.
2. Introduce an 8FR or larger neurovascular balloon guiding catheter.
3. Aided by angiographic fluoroscopy, determine the deployment location and its diameter.

Selectively access the occluded vessel using a microcatheter with a Rotating Hemostatic Valve (RHV) flushed with heparinized saline. With the aid of a guidewire

3.a Advance the microcatheter until the end of the microcatheter is positioned distally to the thrombus, so that the usable length of the Tigris retriever will extend past each side of the thrombus in the vessel. Verify the location of the distal side of the thrombus by injecting contrast media through the microcatheter.

3b. Stenosis identification: A suspected stenosis can be evidenced by difficulty crossing the lesion with a wire, poor expansion of the device, or calcium on a CT image.

3c. Small caliber bifurcation identification: Carefully check whether the target occlusion crosses a small caliber bifurcation. For instance opacification of the collateral vessels might indicate such bifurcation. If the clot occludes a bifurcation, prefer the larger division if possible (for example the inferior division of MCA). Perform a contrast injection through the microcatheter to evaluate the sizing of the branch where the device will be deployed.

4. Remove the Tigris retriever from the tray according to the Figure 2.

[figure not shown]

Figure 2. Removal of the Tigris retriever from the tray.

5. Carefully advance the Tigris retriever until the mesh completely extends from the loading tube.
6. Slowly expand the device by sliding the *Slider* backwards. Do not over inflate. Make sure the device is not damaged.
7. Soak the open mesh in heparinized saline.
8. Deflate the device carefully by advancing the *Slider* until the mesh reaches its minimal form (Figure 3).

[figure not shown]

Figure 3. Mesh in minimal form

9. Pull back until the tip is just inside the end of the loading tube (Figure 4).

[figure not shown]

Figure 4. Tip at the end of the loading tube.

10. Insert the loading tube into the microcatheter's RHV and lock it.
11. Slowly advance about 50cm of the Tigertriever through the loading tube into the microcatheter.
12. Slide the loading device back towards the microcatheter's RHV.
13. Continue slowly advancing the device under fluoroscopic visual control until its tip extends out of the microcatheter.
14. Unsheathe the device slowly while following the tip of the device and distal and proximal markers for accurate deployment.
Important: the proximal marker remains stationary during device expansion while the distal marker and tip move slightly backwards. As a result the proximal marker should be positioned proximally to the thrombus.
15. Under fluoroscopic visual control slowly expand the device by sliding the *Slider* backwards.
If stenosis or a small caliber bifurcation were identified as described in steps 3b and 3c above, use extra attention when expanding the Tigertriever, by slowly expansion and avoiding a maximal expansion.
16. Wait 2 minutes to allow device expansion in the thrombus.
17. Position the microcatheter until it is just proximal to the proximal marker of the device. Tighten the RHV to prevent relative movement between the microcatheter and the device.
18. In cases where resistance during device expansion suggests the presence of atherosclerotic plaque at the site of clot, or that the clot and device are crossing a bifurcation and extending into a smaller caliber artery, care should be used not to apply excessively prolonged deployment expansion force to the device in these locations.

7.3.3 Retrieval

1. Inflate the guide catheter balloon to occluded vessel as specified in Balloon Guide Catheter labeling.
2. Slowly withdraw the microcatheter and the Tigertriever device as a unit to the guide catheter tip while applying aspiration to the guide catheter with a 60cc syringe. If needed, adjust the size of the device under fluoroscopic visual control.

If excessive resistance is encountered during the retrieval partially deflate the device before continuing the retrieval.

If stenosis or a small caliber bifurcation were identified as described in steps 3b and 3c in the above, use extra attention when withdrawing the Tigertriever.

3. Apply vigorous aspiration to the guide catheter using syringe and recover Tigertriever device and microcatheter inside the guide catheter. If needed, partially deflate the device prior to inserting it into the guide catheter. Continue aspirating guide catheter until the device and microcatheter are nearly withdrawn from the guide catheter.
4. Open the guide catheter RHV to allow the microcatheter and device to exit without resistance. Use carefully to avoid interaction with the site of the intervention and to prevent air from entering the system.
5. Aspirate the guide catheter to ensure the guide catheter is clean of any thrombus material.
6. Deflate balloon guide catheter.
7. If additional flow restoration attempts are desired:
 - Clot retrieval with Tigertriever devices may be attempted for up to a total of 3 passes.
 - Each Tigertriever device should only be used for a single pass.
8. If flow is not restored after 3 attempts with Tigertriever devices, a rescue device may be used per SOC.

7.4 24 Hour (-6/+12) Follow-up

- Conduct visit at 24 hours (-6/+12 hours) from time of procedure
- Vital signs assessed
- Record concomitant medications
- Perform and record assessment of NIHSS
- Obtain MRI or CT, per standard of care, to assess intracranial hemorrhage

Note: CT /MRI images will be sent as soon as possible to the Imaging Core Lab for evaluation.

- Record any Adverse Events (AEs), as necessary

7.5 48 Hour (\pm 12h) Follow-up

- Record concomitant medications
- Perform and record assessment of NIHSS
- Record any Adverse Events (AEs), as necessary

7.6 Day 4 or Discharge

- Conduct visit at 4 days from time of procedure. If Subject is discharged prior to 4 days, conduct the follow up visit at time of discharge.
- Vital signs assessed
- Record concomitant medications
- Perform and record assessment of NIHSS
- Perform and record results of mRS using the Rankin Focused Assessment
- Record any AEs, as necessary

NIH Stroke Scale and mRS should be performed by certified Study personnel.

7.7 30 days (\pm 7 days), can be performed over the phone

- Conduct visit at 30 days (\pm 7 days) from time of procedure
- Record concomitant medications
- Perform and record the Barthel Index
- Perform and record the mRS using the Rankin Focused Assessment
- Record any AEs, as necessary

mRS should be performed by certified Study personnel.

7.8 90 days (\pm 14 days)

- Conduct visit at 90 days (\pm 14 days) from time of procedure
- Record concomitant medications
- Perform and record assessment of NIHSS

- Perform and record results of mRS using the Rankin Focused Assessment
- Perform and record the Barthel Index
- Perform and record PRO assessments of health-related quality of life (EQ-5D) and degree of disability (AMC-Linear Disability Scale) - Record any AEs, as necessary

NIH Stroke Scale and mRS should be performed by certified Study personnel.

7.9 Unscheduled Visits

When clinically indicated, unscheduled assessments should be completed with corresponding data documented in the eCRF.

7.10 Adverse Events

Adverse events that occur during participation in the TIGER Study will be recorded. See section 11 for more information on AEs.

Table 4: Schedule of Events

Schedule of Events							
Elapsed time/Study procedures	Baseline	Procedure	24 hours (-6/+12)	48 hours (±12)	Discharge or 4 days	30 (±7) days ^{iv}	90 (±14) days
Informed Consent	X						
Demographics	X ⁱⁱ						
Medical History and Concomitant Medications	X ⁱⁱ						
Time of Stroke Symptoms Onset	X ⁱⁱ						
Brain CT Scan or MRI	X ⁱⁱ		X				
Vital Signs	X ⁱⁱ	X	X		X		
NIH Stroke Scale	X ⁱⁱ		X ⁱⁱⁱ	X	X		X
Premorbid mRS score	X						
mRS score					X	X	X
Clinical Laboratory	X ⁱⁱ						
Time of groin puncture		X					
Cath angiography and clot retrieval ⁱ		X					
mTICI Outcome		X					
Functional activity questionnaire - Barthel Index						X	X
Patient-Reported Outcomes (EQ-5D, AMC-LDS)							X
Prior/concomitant medications	X	X	X	X	X	X	X
AE (including hemorrhage other than sICH)		X	X	X	X	X	X

- i. Pre-procedure and post-procedure angiograms will be analyzed by an unbiased core laboratory to make a final determination about TICI Score.
- ii. Assessment may be completed during prescreening without obtaining informed consent if assessment at initial evaluation is be part of local standard of care.
- iii. NIHSS completed 24h and 48h post procedure. The 48 assessment should be performed at least 12 hours after the 24h assessment.
- iv. possible to be performed over the phone

7.11 Clinical Outcomes Assessment

Assessments to be performed as indicated in Table 4 are as follows:

- National Institutes of Health Stroke Scale (NIHSS): Measures stroke-related neurological deficits through 15-item examination. Must be performed by study personnel certified in NIHSS administration (nihstrokescale.org).
- Modified Rankin Scale (mRS): Measures the global degree of disability or dependence of an individual on an ordinal scale. Must be performed by study personnel (who is not the treating physician) who are trained to conduct the mRS assessment using the standardized Rankin Focused Assessment (RFA)
- Barthel Index: Measures performance of activities of daily living on a 10-item, 0-100 point scale.
- Patient Reported Outcome Assessment (PRO):
 - Academic Medical Center – Linear Disability Score (AMC-LDS): Patient-reported measure of disability status on a linear scale.
 - EQ-5D: Patient-reported measure of health-related quality of life, with brief patient-reported ratings along the 5 dimensions of mobility, self-care, usual activities, pain/discomfort, and affect.

8. STATISTICAL ANALYSIS

8.1 General Principles

The primary analysis cohort will include all data collected for all enrolled Subjects, referred to in International Conference on Harmonization (ICH) document E9, “Statistical Principles for Clinical Trials,” as the *full analysis set*.

Continuous variables will be summarized with standard statistics including the mean, standard deviation, median, interquartile range, and range. Categorical variables will be summarized using frequency tables and cross-tabulations. Statistical analysis will be performed using SAS software version 9.4 or higher (SAS Institute, Cary, NC, USA), R version 3.3 or higher (R Foundation for Statistical Computing, Vienna, Austria) or other validated statistical software.

For the primary endpoint analysis, a P-value of less than 0.05 will be deemed statistically significant. For AE reporting, the primary analysis will be based on Subject counts, not event counts. Both Subject counts and event counts will be presented in tabular summaries of results.

8.2 Primary Endpoints

The primary effectiveness endpoint is successful reperfusion, defined as an mTICI score of 2b or better. The performance goals (PG) for evaluating effectiveness is based on outcomes reported from six recent pivotal studies (TREVO 2, SWIFT, MR CLEAN, ESCAPE, REVASCAT and SWIFT PRIME) evaluating the Solitaire and Trevo stent-retriever devices.

Table 5: Summary of criteria from prior studies used for generation of performance goal.			
Study	Reperfusion using study-specific metric as reported	Metric and threshold employed	Converted to mTICI 2b/3
TREVO 2	68%	Original TICI 2b/3	78%*
SWIFT	69%	TIMI 2/3	76%**
MR CLEAN	59%	Modified TICI 2b/3	59%
ESCAPE	72.4%	Modified TICI 2b/3	73.8%***
REVASCAT	65.7%	Modified TICI 2b/3	65.7%
SWIFT PRIME	88%	Modified TICI 2b/3	88%
Pooled estimate			73.4%

* Adjustment for TREVO 2 is performed using Suh et al. (2013)⁴³, in which 47% (69/146) of cases analyzed and classified as TICI 2a under the oTICI paradigm were found to be TICI 2b under the mTICI paradigm. TREVO 2 results were then adjusted accordingly.

** As reported in secondary publications versus original study endpoint of TIMI 2/3⁴⁴

*** As reported in secondary publication versus original study outcome of oTICI⁴⁵

The PG for the primary effectiveness endpoint of reperfusion post-procedure (mTICI 2b or better) is defined as the incidence in the five trials cited above minus a statistical margin of 10%, the same threshold as in the SWIFT pivotal trial (Saver, 2012, *Lancet*), therefore giving a PG of 73.4% - 10% = 63.4%.

The resulting null and alternative statistical hypotheses are therefore as follows:

$$H_0: p \leq PG$$

$$H_A: p > PG,$$

where $PG = 73.4\% - 10\% = 63.4\%$ as above and p is the observed incidence of reperfusion post-procedure with the Tigertriever Revascularization Device. The hypothesis test will be performed at an overall two-sided alpha level of 0.05 using exact binomial methods, in which the lower confidence bound on the observed incidence of reperfusion is compared to the PG.

The primary safety endpoint is the composite of all-cause mortality at 90 (± 14) days and symptomatic intracranial hemorrhage at 24 hours (18-36h). The performance goal (PG) for evaluating safety is based on outcomes reported from the same six studies as for primary efficacy as employed above.

Table 6: All-cause mortality and sICH for comparable studies.		
Study	All-cause mortality at 90 days	sICH at 24 hours
TREVO2	33%	7%
SWIFT	17.2%	1.7%
MR CLEAN	21%	7.7%
ESCAPE	10%	3.6%
REVASCAT	18.4%	4.9%
SWIFT PRIME	9%	0%
Pooled estimate	18.2%	4.2%

The performance goal (PG) for the composite primary safety endpoint of all-cause mortality and symptomatic intracranial hemorrhage is defined using the incidence of the individual endpoints in the six trials cited above. For this purpose, the sum of the two pooled event rates is $18.2\% + 4.2\% = 22.4\%$; however, as sICH is known to be associated with mortality, this is likely an overestimate of the composite event rate. For conservatism, therefore, only half of the sICH rate will be added to mortality as representing distinct subjects, resulting in a pooled event rate of 20.4% . Adding to this a statistical margin of 10% gives a PG of $20.4\% + 10.4\% = 30.4\%$.

The resulting null and alternative statistical hypotheses are therefore as follows:

$$H_0: p > PG$$

$$H_A: p \leq PG,$$

where $PG = 20.4\% + 10.4\% = 30.4\%$ as above and p is the observed incidence of revascularization post-procedure with the Tigertriever device. The hypothesis test will be performed at an overall two-sided alpha level of 0.05 using exact binomial methods, in which the upper confidence bound on the observed incidence of revascularization is compared to the PG.

The primary endpoint analysis will be performed using the intent to treat (ITT) population. The ITT population will consist of all enrolled subjects who had at least one Tigertriever device attempt/deployment irrespective of major protocol violation. The per protocol (PP) population is defined as ITT patients who do not have major protocol violations. A major protocol violation includes when a subject does not meet inclusion/exclusion criteria. All protocol violations will be reported.

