6. STUDY DESIGN

The TIGER Study is a multi-center, single arm, prospective IDE study. The study will accumulate data in order to evaluate the safety and effectiveness of the Tigertriever mechanical revascularization device.

The study will enroll patients experiencing AIS due to a LVO who are either refractory to or ineligible for IV t-PA treatment. Patients must meet all inclusion criteria and none of the exclusion criteria in order to be enrolled into the study.

Device performance in this study will be compared with criteria performance goal derived from five recent studies of predicate stent-retriever devices, specifically TREVO 2, SWIFT, MR CLEAN, ESCAPE and REVASCAT.

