8.4 Sample Size and Power

With a hypothesized incidence rate of 75% for revascularization post-procedure and desired power of 80%, and using an exact binomial test with a nominal 0.025 one-sided significance level (equivalent to a two-sided $\alpha=0.05$), the required evaluable sample size for primary efficacy is 135. For primary safety, under a hypothesized incidence rate of 20% for the composite endpoint and desired power of 80%, the corresponding required evaluable sample size is 153. As 153 is the larger of these two values, this will be the required evaluable sample size to reach at least 80% power for both effectiveness and safety analyses. Considering a 5% loss to follow-up rate, which is consistent with the observed follow-up rate to date, the Sponsor proposes to adjust the total sample size to 160.

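### Section 8.2: the printed derivation of the safety performance goal is arithmetically false, although 30.4% is recoverable as the goal in use (minor)

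*Combined protocol and SAP*

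**What the plan says.** Section 8.2 says that the safety PG "is based on outcomes reported from the same six studies as for primary efficacy as employed above". Table 6 lists 90-day mortality and 24-hour sICH for those six studies, with pooled estimates of 18.2% and 4.2%. The composite PG "is defined using the incidence of the individual endpoints in the six trials cited above". The text first notes that "the sum of the two pooled event rates is" 22.4%, calls this a likely overestimate because sICH is associated with death, and therefore halves the sICH part: "only half of the sICH rate will be added to mortality as representing distinct subjects, resulting in a pooled event rate of" 20.4%.

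The margin follows: "Adding to this a statistical margin of 10% gives a PG of" 20.4% + 10.4% = 30.4%. The same equation, with 10.4%, is repeated under the hypotheses.

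Section 8.4 uses an exact binomial test at one-sided 0.025, a true composite rate of 20% and 80% power, and states that "the corresponding required evaluable sample size is 153". It does not restate the PG. It then allows for 5% loss to follow-up and sets the total at 160.

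The linked effectiveness sentence in Section 8.2 says that the PG "is defined as the incidence in the five trials cited above minus a statistical margin of 10" percent. Section 6 describes the PG as "derived from five recent studies of predicate stent-retriever devices, specifically TREVO 2, SWIFT, MR CLEAN, ESCAPE and REVASCAT". Table 5 has six rows, including SWIFT PRIME.

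**The concern.** The PG is the pass/fail line for the primary safety endpoint, and safety sets the sample size. A reader who follows the plan's own numbers does not arrive at 30.4%: the stated rule applied to the printed inputs gives 30.3%, and the printed formula gives 30.8%. Whoever programs the final analysis should not have to guess which element is the error. Read literally, the formula would move the decision limit by one event at the planned numbers.

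**Working it through.** **Inputs.** Section 8.2 and Table 6: pooled mortality 18.2%, pooled sICH 4.2%, half of sICH added, margin 10% (words) or 10.4% (formulas). Section 8.4: exact binomial, one-sided 0.025, true rate 20%, power 80%, 153 evaluable, 5% loss, total 160.

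**1. The composite rate.** 18.2 + 4.2/2 = 18.2 + 2.1 = 20.3%; the plan prints 20.4%.
- Rounding: values that round to 18.2 and 4.2 allow sums from 18.15 + 4.15/2 = 20.225 to 18.25 + 4.25/2 = 20.375. Printing 20.4 needs at least 20.35, the top of that range.
- Simple means of the six Table 6 rows: mortality (33 + 17.2 + 21 + 10 + 18.4 + 9)/6 = 18.10%; sICH (7 + 1.7 + 7.7 + 3.6 + 4.9 + 0)/6 = 4.15%. These give 18.10 + 2.075 = 20.175%, so the printed 18.2% is not the simple mean of the printed rows. Several rows are whole percentages, which could account for this, but the pooling method is not stated.

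**2. The margin.** 20.4 + 10.4 = 30.8; 20.4 + 10 = 30.4; 20.3 + 10 = 30.3; 20.175 + 10 = 30.175, or about 30.2.

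**3. Which PG did Section 8.4 use?** Event limit = largest x with P(X ≤ x | n, PG) ≤ 0.025. Power = P(X ≤ x | n, 0.20). Required n is taken as the smallest n from which power stays at or above 80%. The plan does not state this criterion. It is inferred because it also reproduces the effectiveness figure of 135 (PG 63.4%, true rate 75%).

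| PG | Required n | Limit and power at 152 | Limit and power at 153 | Limit and power at 160 |
|---|---|---|---|---|
| 30.2% | 158 | 34, 79.9% | 34, 78.7% | 36, 81.4% |
| 30.3% | 158 | 34, 79.9% | 34, 78.7% | 36, 81.4% |
| 30.4% | 153 | 34, 79.9% | 35, 83.9% | 36, 81.4% |
| 30.8% | 144 | 35, 84.9% | 35, 83.9% | 37, 86.1% |

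Of these four, only 30.4% returns the plan's 153.

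**4. Loss to follow-up.** 160 × 0.95 = 152, one below 153. Conversely, 153/0.95 = 161.05.

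**5. Number of source studies for effectiveness.** Mean of all six Table 5 rows: (78 + 76 + 59 + 73.8 + 65.7 + 88)/6 = 73.4%, as printed. Without SWIFT PRIME: 352.5/5 = 70.5%. The 63.4% goal therefore rests on six studies.

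**The case against.** The strongest reply is that the threshold is not in doubt. The plan prints 20.4%, states a 10% margin in words and prints 30.4% twice, and 20.4 + 10 = 30.4. The step from 20.3 to 20.4 could be rounding of unrounded rates, and the decision limit at 152 or 160 subjects is the same either way. All of this stands, and it is why the point is minor. It does not make the printed equation true, and the plan does not show the unrounded rates.

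Three stronger readings are tempting, and the documents do not support them:

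- **That the margin was widened to 10.4%, or that the PG is 30.8%.** The words say 10%, the result is printed as 30.4% both times, and a PG of 30.8% would give 144 rather than 153. The 10.4% is a misprint.
- **That the correct PG is 30.3%.** This takes the rounded pooled rates as exact. Simple means of the Table 6 rows point to about 30.2%, and unrounded pooled rates might support 30.4%. The documents do not settle which.
- **That the trial is too small because 158 evaluable are needed.** That figure applies only if the PG is 30.2% or 30.3%, and only under the inferred criterion. Exact power is saw-toothed: at 30.3% it first reaches 80% at n = 142, and at n = 154 it is 82.9%. The plan asks only for 80% power and states no rule for the dips.

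**Conclusion.** The point holds as an error of derivation and documentation, at minor severity. Two figures in Section 8.2 are wrong as printed: 20.4% does not follow from 18.2% and 4.2%, and 10.4% stands in both formulas where 10% is meant. The operative PG is 30.4%; the support from the match at 153 rests on the inferred power criterion, while the stated 10% margin and the twice-printed result do not.

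The practical effect is nil at 152 and 160 evaluable subjects for any PG from 30.2% to 30.4%. At exactly 153, moving from 30.4% to 30.3% lowers the limit from 35 to 34 events. A literal 30.8% would allow 35 instead of 34 at 152, and 37 instead of 36 at 160.

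The shortfall of 152 against 153 is real but marginal: 79.9% power against a target of 80%, at a true rate of 20%. The five-versus-six discrepancy is a wording matter and leaves the effectiveness PG of 63.4% unaffected.

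**What to change.** Before database lock:

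1. In Section 8.2, replace 10.4% with 10% in both safety formulas.
2. State how the Table 6 rates were pooled, and give the unrounded values behind 18.2%, 4.2% and 20.4%. If they support 20.4%, confirm 30.4% as the agreed PG. If not, state the PG that they do give and agree it with the regulator; the change summary for Revision 02 records that the PG was revised after an FDA letter. In that case the 153 in Section 8.4 would also need replacing.
3. In Section 8.4, note that 160 less 5% is 152. Restate safety power as 79.9% at 152 evaluable (34 or fewer events passes) and 81.4% at 160 (36 or fewer). These figures hold for a PG of 30.2%, 30.3% or 30.4%.
4. Say six rather than five trials in the effectiveness PG sentence, and add SWIFT PRIME to the list in Section 6.

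If the unrounded rates support 30.4%, the cost is wording only. If they do not, add a regulatory exchange and a corrected sample-size statement. Neither case needs extra enrolment, provided that the sponsor accepts 79.9% power at 152 in place of the claim of at least 80%.

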	
proximal vessel requiring treatment or preventing device access to the thrombus (for example, stenosis or occlusion in the cervical internal carotid artery).
 
 16. Females who are pregnant or breastfeeding. 17. Known current use of cocaine at time of treatment. 18. Prior recent stroke in the past 3 months. 19. Renal failure with serum creatinine >3.0 or Glomerular Filtration Rate (GFR) <30. 20. Known cerebral vasculitis. 21. Rapidly improving neurological status defined as improvement of greater than 8 points on the NIHSS or improvement to NIHSS of < 6 prior to procedure 22. Clinical symptoms suggestive of bilateral stroke or stroke in multiple territories. 23. Ongoing seizure due to stroke. 24. Evidence of active systemic infection. 25. Known cancer with metastases. 26. Suspicion of aortic dissection, septic embolus, or bacterial endocarditis. 27. Evidence of dissection in the extra or intracranial cerebral arteries. 28. Occlusions in multiple vascular territories (e.g., bilateral anterior circulation, or anterior/posterior circulation). 29. Aneurysm in target vessel.

Study Duration
	
Enrolment: approximately 24 months
 
Follow-up period: 3 months

Statistical Analysis
	
The primary efficacy endpoint, defined as successful reperfusion with the Tigertriever device, will be tested against a performance goal (PG) derived from adjudicated trial data for similar devices.
 
The primary safety endpoint, defined as the composite of all-cause mortality at 90 days and symptomatic intracranial hemorrhage (sICH) at 24 hours, will be tested against a performance goal (PG) derived from the same set of trials.
 
Secondary efficacy and safety endpoints will not be subject to hypothesis testing but will be examined using confidence intervals to characterize the relevant population parameter.

Schedule of Events							
Elapsed time/Study procedures	Baseline	Procedure	24 hours (-6/+12)	48 hours (±12)	Discharge or 4 days	30 (±7) days	90 (±14) days
Informed Consent	X						
Demographics	X						
Medical History and Concomitant Medications	X						
Time of Stroke Symptoms Onset	X						
Brain CT Scan or MRI	X		X				
Vital Signs	X	X	X		X		
NIH Stroke Scale	X		X	X	X		X
Premorbid mRS score	X						
mRS score					X	X	X
Clinical Laboratory	X						
Time of groin puncture		X					
Cath angiography and clot retrieval		X					
mTICI Outcome		X					
Functional activity questionnaire- Barthel Index						X	X

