3.2 Safety Endpoints

3.2.1 Primary Endpoint

- Composite of all-cause mortality at 90 (± 14) days and symptomatic intracranial hemorrhage (sICH) within 24 (18-36) hours of the study procedure. Symptomatic intracranial hemorrhage (sICH) shall be defined as any parenchymal hematoma type 2, remote intracerebral hemorrhage, subarachnoid hemorrhage, or intraventricular hemorrhage that is the predominant cause of ≥ 4 point NIHSS deterioration at 24 hours

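### Section 8.2 states the primary safety test in terms of revascularization instead of the death/sICH composite

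*Combined protocol and SAP*

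**What the plan says.** Section 8.2 opens its safety part correctly: "The primary safety endpoint is the composite of all-cause mortality at 90" days together with sICH at 24 hours. The goal "for the composite primary safety endpoint of all-cause mortality and symptomatic intracranial hemorrhage is defined using the incidence of the individual endpoints", as reported by six reference trials.

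After the safety hypotheses are displayed, the text changes variable. It defines p as "the observed incidence of revascularization post-procedure with the Tigertriever device" and describes an exact binomial test at two-sided 0.05 "in which the upper confidence bound on the observed incidence of revascularization is compared to the PG".

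The other places that describe the safety test or endpoint use the composite:

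- Section 3.2.1 lists 90-day all-cause mortality "and symptomatic intracranial hemorrhage (sICH) within 24 (18-36) hours of the study procedure".
- The Protocol Summary, under Statistical Analysis, says the "composite of all-cause mortality at 90 days and symptomatic intracranial hemorrhage (sICH) at 24 hours, will be tested against a performance goal".
- Section 8.4 sizes the safety test "under a hypothesized incidence rate of 20% for the composite endpoint and desired power of 80%, the corresponding required evaluable sample size is 153".

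On the PG value, section 8.2 says "Adding to this a statistical margin of 10% gives a PG of" and then prints 20.4% + 10.4% = 30.4%. The clause that defines p repeats the same sum.

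The Study Design row of the Protocol Summary still describes safety as all-cause mortality alone, although the Primary Endpoints row of the same table gives the composite.

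**The concern.** Section 8.2 is the only place that says which confidence bound, on which quantity, decides the confirmatory safety test. The synopsis says only that the composite is tested against a PG. The variable is wrong both in the definition of p and in the decision sentence, and nothing later in the plan corrects it.

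The literal rule also points the wrong way: a device that seldom restores flow would pass safety, and one that meets the effectiveness goal would fail. In addition, section 8.9 requires any departure from the planned methods to be documented with a rationale. As the text stands, testing the intended composite would itself be such a departure.

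The misprinted sum sits in the same clause and leaves two candidate values for the PG, 30.4% and 30.8%.

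**Working it through.** **Inputs.** Safety PG 30.4% and effectiveness PG 63.4% (section 8.2). Assumed composite rate 20%, assumed revascularization rate 75%, one-sided 0.025, 80% power, 153 evaluable, 160 total (section 8.4). Counts at n = 160 assume that all 160 subjects are evaluable.

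**Rules.** Safety passes with X ≤ c events, where c is the largest count with P(X ≤ c | n, PG) ≤ 0.025. Effectiveness passes with X ≥ r, where r is the smallest count with P(X ≥ r | n, 63.4%) ≤ 0.025. These match comparing the exact (Clopper-Pearson) 95% limit with the PG. Exact power moves in a saw-tooth, so N is taken as the smallest value from which power stays at or above 80%.

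**1. Reproduce the plan's figure with the composite as X.** With PG 30.4% and a true rate of 20%, power first reaches 80% at n = 142 and stays there from n = 153. At n = 152 it is 79.9%. The plan's 153 is reproduced exactly. The effectiveness figure of 135 is reproduced by the same method.

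**2. Critical values of the intended safety rule.**

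| n | Pass if events ≤ | Exact alpha | Power at 20% | Upper 95% limit at cut-off |
|---|---|---|---|---|
| 153 | 35 (22.9%) | 2.4% | 83.9% | 30.35% |
| 160 | 36 (22.5%) | 1.7% | 81.4% | 29.76% |

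**3. Apply the sentence as written, with revascularization as X.** At n = 160:

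- Effectiveness needs at least 114 reperfused: 114/160 = 71.3%, lower limit 63.57%, above 63.4%.
- Literal safety needs at most 36 reperfused: 36/160 = 22.5%.
- No count is both at least 114 and at most 36.
- At the planned 75% (120/160), the upper limit is 81.5%, against 30.4%.

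At n = 153 and a true rate of 75%, the chance of passing the literal safety rule is about 2 × 10⁻⁴¹.

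**4. The printed sum.** 20.4% + 10.4% = 30.8%, whereas 20.4% + 10% = 30.4%. Repeating step 1 with PG 30.8% gives N = 144, not 153, so 30.4% is the value the design used. The two values separate at n = 160: 37/160 has an upper limit of 30.44%, which fails 30.4% and passes 30.8%. At n = 153 the cut-off is 35 under either value.

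**The case against.** The strongest reply is that nobody would be misled. The correct variable stands in section 3.2.1, the synopsis, section 8.4 and the paragraph of section 8.2 just before the faulty sentence. No analyst would compare a reperfusion rate with a goal built from mortality and sICH rates. On this view the literal-rule figures only show that the sentence cannot be meant, and the slip is editorial. That stands as far as it goes: the intent is clear, and no design quantity is affected. It does not remove the need to correct the operative sentence of a primary test.

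The misprinted margin also has limited reach. The plan states 10% in words and 30.4% as the result, 30.8% appears nowhere, and the cut-off at n = 153 is the same under either value.

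The wording looks adapted from the effectiveness test, but that is an inference. The parallel effectiveness sentences in section 8.2 say reperfusion, while revascularization is the term section 8.4 uses for effectiveness.

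Two neighbouring details are separate from this point. The displayed safety alternative includes equality with the PG. The printed inputs give 18.2% + 2.1% = 20.3%, not 20.4%, which unprinted decimals could explain.

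**Conclusion.** The point holds. Section 8.2 names the wrong variable twice in the primary safety test. As written, the rule cannot be met by any device that meets the effectiveness goal: at most 36 against at least 114 reperfused of 160. The intended rule is not in doubt. With the composite as the variable, a PG of 30.4% and a true rate of 20%, the exact calculation returns the plan's own 153, with cut-offs of 35/153 and 36/160. The 10.4% addend is a misprint for 10%.

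This is a text error, not a design flaw, and it should be corrected before the analysis. The cut-offs assume the exact test at one-sided 0.025 in section 8.4 and the evaluable numbers shown.

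**What to change.** In section 8.2, replace the clause defining p and the decision sentence with text such as:

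> where PG = 20.4% + 10% = 30.4% and p is the true proportion of subjects with all-cause death by 90 (±14) days or sICH within 24 (18-36) hours of the procedure. Safety is met if the upper limit of the exact two-sided 95% confidence interval for this proportion is below 30.4%.

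Print 10% instead of 10.4% in the PG derivation sentence as well. In the same edit, put equality with the PG in the null hypothesis so that it agrees with the strict rule, and confirm the unrounded inputs behind 20.4%. In the Study Design row of the Protocol Summary, replace the mortality-only description of safety with the composite.

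The cost is a few words in section 8.2 and one synopsis entry. N, PG, critical values and data collection do not change.
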